**Protocol Revision History**

Version Date	Revision Summary
19 January 2021	Initial Approval Version
14 February 2021	Addition of Drs. [name] and [name] as sub-investigators.
19 February 2021	

• Addition of baseline and follow-up blood draws that includes an electrolyte panel, BUN, Cr, ALT, and AST; serum pregnancy test at baseline

• Addition of effective birth control instruction

10 June 2021	

• Addition of NIOSH red flag guideline (an increase in hearing threshold level of 15 dB or more at any frequency (2, 3, 4, 6 kHz) in either ear for permanent threshold shift as a secondary endpoint.

• Change in sample size

• Removal of saliva collection and inclusion of blood draw for DNA analysis.

• Inclusion criteria corrected.

• Addition of primary and secondary efficacy measures to study design (section 4.0)

• Added detail and updated modifications to tests within scheduled assessments (section 5.1) and follow-up assessments (5.5)

• Updated cognitive test section to reflect specific measures being used (5.0)

• Clarified wording for evaluability section (section 6.0)

• Removed NEQ and HHIA Questionnaires from appendix and assessment (5.0) section

• Added 1-Minute Noise Screen Questionnaire to appendix and assessment section (5.0)

• Corrected timing of evaluation for post-dose drug related adverse events from 2 weeks to 30 days (6.0)

• Delineated and updated study calendar to reflect each visit for when assessments and questionnaires are administered (9.0)

• Clarified which assessments would be administered at what visit in each of the assessment sections (screening, baseline and follow-up visits) (5.0)

	
 
• Removed PI and Sub-Investigator information (cover page)
 
• List protocol version as a separate line (cover page)
 
• Name change of form “Audiologic and Medical History” to “Case History”.
 
• Clarification of when clinical ear exam will be performed (5.0, 9.0)
 
• Statistical Considerations section updated to match SAP (12.0)
 

21 October 2021	
 
• Inclusion of stratification table for noise exposure (5.2)
 
• Randomization language updated (4.0)
 

09 November 2021	
 
• Clarification of language for secondary outcomes analysis criteria
 

21 January 2022	
 
• Addition of section “Blood collection, transportation, and storage”
 

23 March 2022	
 
• Addition of audiology language in situations of an absence of a threshold.
 

## **1.0 BACKGROUND AND SIGNIFICANCE**

### **1.1 Noise-induced hearing loss (NIHL)**

Noise-induced hearing loss (NIHL) is a serious problem. When a service member leaves the military, hearing loss can impact his or her quality of life and employability (Pfannenstiel, 2014). Service members are vulnerable to two types of NIHL: occupational NIHL due to continuous or intermittent noise exposure and acoustic trauma due to a sudden burst of sound. Because no form of hearing protection offers complete protection against noise of that intensity, repeated firing of weapons even with ear protection devices can subsequently lead to occupational NIHL (Chen and Brueck, 2011). Almost every member of the armed forces will be exposed to hazardous noise at some point in his or her career (McIlwain et al., 2008; Kirchner et al., 2012; Yankaskas, 2013), highlighting the urgent need for pharmaceutical intervention. Despite positive outcomes in preclinical studies, to date, no drugs have been approved by the U.S. Food and Drug Administration (FDA) for use in the amelioration of NIHL (Le Prell and Bao, 2012; Mukherjea et al., 2015).

### **1.2 NIHL and its Pathogenesis**

After noise exposure, two phases of hearing loss can be measured. The first is a temporary threshold shift (TTS), which is greatest immediately after noise exposure, and gradually lessens within the first 24 hours. The second phase is a permanent threshold shift (PTS), which is measured two to three weeks after noise exposure (for recent review, Ryan et al., 2016; Liberman, 2016). These changes are typically monitored using behavioral pure-tone thresholds, distortion product otoacoustic emissions (DPOAE), or the auditory brainstem response (ABR) to generate an audiogram (a plot of threshold as a function of test frequency). The noise-induced damage is dependent on the noise pattern, intensity, and duration, with longer and louder noises being more hazardous than shorter or quieter sound exposures (Wang et al., 2002; Harding and Bohne, 2007; Chen et al., 2015). In addition, NIHL susceptibility differs markedly among individuals, resulting from the interaction of genetic and environmental factors (Clifford et al., 2016; Groth et al., 2016; Lavinsky et al., 2016). For example, in animals, the C57BL/6J mouse strain is more susceptible to noise than other mouse strains (Davis et al., 2001). In humans, individuals with specific single nucleotide polymorphisms (SNPs) in genes for certain antioxidant enzymes may be more susceptible to NIHL (Lin et al., 2009) and a recent study developed a genetic risk score for the likelihood of NIHL based on genetic markers (Zhang et al., 2019). Over 100 loci associated with syndromic and non-syndromic hearing loss provide excellent biomarkers for PGx studies and are easily surveyed in genetic screening protocols (e.g. Pawelczyk et al., 2009; Konings et al., 2009; Grondin et al., 2015). Furthermore, known genetic variation is associated with the metabolism of anti-epileptic drugs including zonisamide (Saruwatari et al., 2010) and could be used to predict patient populations that are both responsive and non-responsive to drug treatments.

Finally, methodologies are currently under development to predict genotypic variation based on audiographic profiles that could in practice be integrated with genetic data (<https://audiogene.eng.uiowa.edu/>) facilitating the statistical analysis of drug efficacy in clinical trials.

NIHL is caused by sensorineural damage, primarily to the sensory hair cells and primary auditory neurons of the cochlea (Liberman, 2017). Outer hair cells (OHCs) are particularly sensitive to noise. When OHCs are damaged, hearing thresholds increase due to a loss in amplification of the cochlear signal. Recently, Kujawa and Liberman (2006, 2009) have expanded on these classic findings with the observation that certain noise exposures at “benign” levels to rodents can result in only TTS, but no PTS. Nevertheless, the animals show selective synaptic loss between inner hair cells (IHCs) and spiral ganglion neurons (SGNs) with high thresholds, ultimately accelerating hearing loss over time. Because this cochlear synaptopathy does not change the hearing threshold immediately, the term “hidden hearing loss” has been used to label the hidden synaptopathic injury, and this term has also been used to describe corresponding functional deficits that are assumed to be hidden behind the normal hearing threshold.

Clinically, difficulties with understanding speech in noise have long been observed in older adults with normal audiometric thresholds (e.g. Frisina and Frisina, 1997). Loss of fidelity in the encoding of suprathreshold signals may provide one explanation for this deficit (Sergeyenko et al., 2013; Tremblay et al., 2015). Thus, there is the potential for profound functional consequences after a so-called benign noise exposure that led to only TTS. Of particular concern for military personnel with the potential for repeat exposure (Davis, 2016; Bramhall et al., 2017), further studies have found that benign noise exposures resulting in only TTS can also contribute to PTS after repeated exposure (Wang and Ren, 2012), underpinning the importance of developing pharmaceutical interventions to prevent noise-induced cochlear synaptopathy for military service members.

### **1.3 Molecular Pathways Underlying NIHL**

Although mechanical destruction and decreased blood flow contribute to NIHL (Quirk et al., 1991; Mulroy et al., 1998), several key molecular mechanisms such as signaling mediated by an ATP receptor have been identified to contribute to TTS (for recent review, see Kurabi et al., 2017). Common mechanisms underlying both TTS and PTS have also been identified. One is the increase of mitochondrial free radical formation such as reactive oxygen species (ROS) due to noise-induced intense metabolic activity in the cochlea (e.g., Yamane et al., 1995; Ohlemiller et al., 1999; Ohinata et al., 2000; Henderson et al., 2006; Campbell et al., 2007; Darrat et al., 2007). Thus, it is not surprising that attempts to prevent NIHL with antioxidant agents have become the focus of much research in this field (Seidman et al., 1993; Hight et al., 2003; McFadden et al., 2005; Yamashita et al., 2005; for review, see Le Prell and Lobarinas, 2015). However, most of these interventions have been only partially effective or ineffective in preventing NIHL (Lynch and

Kil, 2005; Campbell et al., 2007; Kopke et al., 2007; Le Prell et al., 2007). The largely disappointing outcomes may be due to a narrow therapeutic window. As ROS signaling is also important for normal cellular function (for recent review, Sbodio et al., 2018), high doses of antioxidants may have less therapeutic benefit (for example, Kil et al., 2017). Recently, new signaling pathways underlying NIHL have been identified, including deregulation of calcium homeostasis (Guitton et al., 2004; Zine and Van De Water, 2004; Chen et al., 2012; Han et al., 2015; Chen et al., 2015). Deregulation of calcium signaling may contribute to development of both TTS and PTS. In addition, calcium signaling is upstream of many other cellular survival signaling pathways. For example, it can control ROS signaling by regulating the release of ROS from the mitochondrion (Esterberg et al., 2013, 2014). Calcium homeostasis in the cochlea can be regulated by several types of calcium channels, which include voltage-gated calcium channels (VGCCs) (Rodrigues Contreraz and Yamoah, 2001; Adamson et al., 2002; Fuchs, 2002; Schnee and Ricci, 2003). VGCCs can be divided into two groups: high-voltage-activated calcium channels and low-voltage-activated calcium channels (Igelmund et al., 1996; Lacinova et al., 2000; Perez-Reyes, 2003; Yunker and McEner, 2003). The family of low-voltage-activated, or T-type, calcium channels (Cav3) is composed of three members (Cav3.1, Cav3.2, and Cav3.3) based on their respective main pore-forming alpha subunits:  $\alpha$  1G,  $\alpha$  1H, and  $\alpha$  1I (Perez-Reyes, 2003; Yunker and McEner, 2003). Our studies on drug repurposing have shown that a family of antiepileptic drugs blocking T-type calcium channels can prevent and treat NIHL (Shen et al., 2007; Bao et al., 2013). We have also determined the expression pattern of these calcium channels in the cochlea. All subtypes are present in SGNs, and  $\alpha$  1G and  $\alpha$  1I are expressed in the hair cells and supporting cells (Shen et al., 2007). Thus, it is not surprising that an antiepileptic drug (AED), zonisamide (ZNS), which blocks T-type calcium channels, has both prophylactic and therapeutic functions against NIHL (Bao et al., 2013). In addition, epidemiological studies show that ZNS is well-tolerated even for long-term treatment (Hashimoto et al., 1994; Leppik, 2006, White et al., 2010). These findings have led us to this project, which is the repurposing ZNS against NIHL for military service members.

#### 1.4 NIHL and Pharmacogenetics

*Preliminary results.* Pharmacogenetics (PGx) is the study of how a person's genetic makeup determines his or her response to a therapeutic intervention. It offers the promise of utilizing genetic fingerprints to predict an individual's responses to drugs in terms of safety, efficacy, and pharmacokinetics. It can revolutionize the practice of medicine by individualizing treatment through the use of novel diagnostic tools.

Here, we provide three types of data from our PGx study of age-related hearing loss. They are highly pertinent because the same approaches will be applied to this project. First, we describe our recent clinical findings on the delay of ARHL in human subjects taking calcium channel blockers (CCBs). Second, we present our

[figure not shown]
preliminary human genetic studies of ARHL in the same population based on the continuous extreme phenotypes (CEP) and sequence kernel association test (SKAT) approaches. Third, we present an estimate of patient populations using the CEP-SKAT method.

**Delay of ARHL in patients taking CCBs.**

In our preliminary study, a total of 35 white female patients have completed their first visit, with 26 of them using amlodipine (74%) for more than one year. We compared this CCB group with two control cohorts, also of white females: control 1 group (Con 1) from the Rochester, NY, area (447 participants) and control 2 group (Con 2) from the St. Louis, MO, area (55 participants) (Fig. 1).

Since ARHL starts at higher frequencies in the cochlea, we divided audiograms into three pure tone averages (PTA): averages of 0.25, 0.5, and 1 kHz (PTAL); averages of 2 and 4 kHz (PTAH24); and averages of 2, 4, and 8 kHz (PTAH248). The means for the CCB group were: PTAL (15.1 dB HL), PTAH24 (20.7 dB HL), and PTAH248 (24.0 dB HL), and the means for the control 1 group were: PTAL (20.1 dB HL), PTAH24 (30.7 dB HL), and PTAH248 (35.2 dB HL).

Since there were no data for 8 kHz for the control 2 group, the means for this group were PTAL (20.7, dB HL) and PTAH24 (29.3 dB HL). The two-tailed unequal variance t-test showed a significant difference between the CCB and the control 1 group for PTAL ( $p = 0.00067$ ), PTAH24 ( $p = 0.00001$ ), and PTAH248 ( $p = 0.00021$ ), and a significant difference between the CCB and control 2 groups for PTAL ( $p = 0.02777$ ) and PTAH24 ( $p = 0.00959$ ). To correct for possible influences from both age and the three cohort sites, we used multivariate regression models with the Bonferroni correction method (Table 1, 2 and 3 for PTAL, PTAH24 and PTAH248, respectively). No significant difference was observed for PTAL between the CCB and control 1 or 2 groups (Table 1), or

**Fig. 1. CCB protection against ARHL.**  
Participants taking CCBs show better hearing thresholds than participants taking no CCBs even at low frequency regions (0.25 to 1 kHz).

**Table 1. Least Squares Means with Bonferroni Correction Model 1**

Cohort	LS Mean	Vs. Control 1	
		p-value	p-value
CCB	19.77	1.0000	.9202
Control 1	20.28		.0784
Control 2	17.50		

**Table 2. Least Squares means with Bonferroni Correction Model 2**

Cohort	LS Mean	Vs. Control 1	
		p-value	p-value
CCB	28.17	.0420*	1.0000
Control 1	35.19		.11
Control 2	28.54		

**Table 3. Least Squares Means with Bonferroni Correction Model 3**

Cohort	LS Mean	Vs. Control 1	
		p-value	
CCB	32.41	.0145*	
Control 1	39.28		

PTAH24 (**Table 2**) between the CCB and control 2 group. However, statistically significant differences were found for both PTAH24 and PTAH248 between the CCB and control 1 group (**Table 2 and 3**). These data indicate CCB had beneficial effects against peripheral ARHL.

The goal of this study is to increase the sensitivity of our clinical trial by identifying subgroups sensitive to NIHL prevention or treatment by ZNS. The expected high variability in individual responses to ZNS against NIHL is dependent on known factors such as age, sex, and previous hearing loss history, all of which are considered in the health survey during the initial screening process. However, unknown genetic variations in the participants can contribute to additional variable responses to ZNS against NIHL. PGx is the ideal approach to address this issue. Based on our preliminary studies, even with the sample size limitation, extreme ZNS protection phenotypes could still be identified, and sampling these individuals can enrich the presence of associated genetic variants. However, the dichotomization procedure used for most extreme phenotype sampling can reduce the analysis power due to a loss of sample size. The CEP-SKAT method can be used to avoid this issue by using continuous phenotypes in the analysis of extreme phenotype samples (Li et al., 2011; Barnett et al., 2012). Therefore, we will use this CEP-SKAT method to analyze our samples.

Pharmacogenetic testing will be performed by the Washington University School of Medicine Genome Technology Access Center.

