## **5.0 SCHEDULED ASSESSMENTS**

### **5.1 Screening (Visit 1) and Baseline (Visit 2) Assessments**

The screening assessment (Visit 1) will occur within 3 months of the first training session. The baseline assessment (Visit 2) will occur within one week of the first training following commencement of the study. These assessments will include the following tests or procedures:

1. Documentation of demographic information, including gender, age, allergies, and current medications (screening visit 1).
2. Clinical examination of the ears (screening and baseline visit 1 and 2).
3. Documentation of key clinical data such as confirmation of thresholds being  $\leq 25$  dB HL up to 4 kHz,  $\leq 30$  dB HL at 4 kHz, and  $\leq 45$  dB HL at 6 and 8 kHz, and the absence of any ear disorder (screening visit 1).
4. Blood draw for laboratory testing that include a serum pregnancy test\*, electrolyte panel, BUN, Cr, ALT, and AST and DNA analysis will be collected (baseline visit 2).

\*Women capable of becoming pregnant will be asked to have a pregnancy test before beginning this study. Women capable of becoming pregnant will be instructed to use effective birth control methods and not to become pregnant while participating in this study as there may be unknown risks to the unborn child. There may be long-term effects of the treatment being studied that could increase the risk of harm to an unborn child. The study team must be notified if the birth control method fails while on the study and/or if the participant becomes pregnant while participating in this research study.

5. Audiogram, ECochG, DPOAE, and WIN testing to document baseline measurements (baseline visit 2).

**Audiometry:** The audiogram will be performed to look for TTS and PTS. Earphones will be placed over the participant's ears and a series of tones at a soft volume will be played at varying frequencies. The participant indicates that they hear the tones by pressing a button. Thresholds will be measured from .025-16 kHz. If there is an absence of a threshold at the limits of the equipment, the threshold will be reported as equipment limits (in dB HL) + 10 dB HL. As with the DPOAE, all equipment and procedures are based on a clinically approved protocol. Each ear will be tested separately.

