## **12.5 Pharmacogenetic analysis plan**

This analysis will be performed at the end of the trial by Gateway Biotechnology. To identify genetic variants with ZNS protection against hearing loss, we will first use univariate logistic regression analyses to identify potential confounding variables: sex, age, Z-scores of drug concentration, Z-scores of noise intensity and duration, and Z-scores of hearing functions measured immediately following range shooting. Single-marker allelic association analyses will be conducted on the two imputed data sets in PLINK v1.07. The data will be analyzed with a logistic regression model on the additive continuous dosage of minor alleles from 0 to 2 to account for uncertainty of imputation. We will combine association results in the two cohorts by performing a genome-wide inverse-variance weighting meta-analysis using PLINK v1.07, and assuming a fixed-effect model. Functional annotation of top-associated markers will be performed with R package NCBI2R 1.4.6 (<http://CRAN.Rproject.org/package=NCBI2R>), and key regional association plots of meta-analyzed results will be generated. To confirm whether these variants are specific to ZNS response, we will apply CEP SKAT to analyze genetic associations based on Z-scores of audiogram average threshold shifts and DPOAE amplitudes. All genetic variants, including both common and rare variants, will be included in this association study. Age, gender, drug concentration, and noise duration and intensity will be adjusted for the analysis. The analysis will also be performed using hearing data collected two to four weeks after range shooting. The only differences will be a) using the Z scores of ECochG AP amplitude, latency, and width as well as WIN score, and b) using average audiogram threshold shifts and DPOAE amplitudes at 30 days (+/- 3 days) post-treatment. To control for confounding effects, these models will be adjusted for age, gender, drug concentration, and noise duration and intensity. Finally, the control and ZNS-treated comparisons will be performed using post-hoc comparisons with a Bonferroni adjustment for multiple comparisons of any ZNS versus none.

Statistical analyses will be performed using the CEP-SKAT method in R language, and the statistical software SAS version 9.4 for Windows will be used for additional analysis.

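### The genome-wide single-marker scan uses logistic regression on an unnamed yes/no outcome, although the plan already derives a continuous threshold shift that would carry more information

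*Protocol*

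**What the plan says.** Protocol 1.4 warns that in extreme-phenotype work "the dichotomization procedure used for most extreme phenotype sampling can reduce the analysis power due to a loss of sample size". It offers the remedy that "The CEP-SKAT method can be used to avoid this issue by using continuous phenotypes in the analysis of extreme phenotype samples" and concludes: "Therefore, we will use this CEP-SKAT method to analyze our samples".

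Protocol 12.5 sets out the analysis in this order, and SAP 7.1.3 follows the same sequence:

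1. Single-marker tests: "The data will be analyzed with a logistic regression model on the additive continuous dosage of minor alleles from 0 to 2". The word continuous here describes the allele dosage, which is the predictor, and not the phenotype. The outcome is not named in either document.
2. Results are combined by "performing a genome-wide inverse-variance weighting meta-analysis using PLINK v1.07".
3. "Functional annotation of top-associated markers will be performed".
4. To check specificity to ZNS response, "we will apply CEP SKAT to analyze genetic associations based on Z-scores of audiogram average threshold shifts and DPOAE amplitudes". Both documents then say that common and rare variants are all included.
5. The analysis is repeated with later hearing data, including average threshold shifts at 30 days.

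The pharmacogenetic link is part of the secondary objectives (Protocol 2.2, SAP 2.2.2). SAP 3.4 lists the DNA analysis as exploratory.

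**The concern.** Section 1.4 asks for a continuous phenotype in order to protect power. The stage that ranks single markers and sends the best of them to annotation uses a model that can only take a categorical outcome. The plan contains no single-marker test of the continuous shift. The CEP-SKAT step that does use the shift tests sets of variants, and annotation is described only for markers from the logistic scan.

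With 132 officers the analysis is short of information from the start, and Protocol 1.4 itself concedes that the sample size is limited. The ranking step would use the less informative of two phenotypes that the trial already has. The unnamed outcome is a gap of its own, since a genome-wide scan cannot be reproduced if its phenotype is not stated.

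**Working it through.** **The plan's own figure.** Neither document gives power, alpha or an information figure for the pharmacogenetic analysis. The PTS rates needed here come from Protocol 12.3 and SAP 2.7: 50% on placebo, 25% on ZNS, 66 per group, one-sided 0.025, power 80.5%. An exact enumeration of the one-sided Fisher test gives 81.3%, and the arcsine approximation with continuity correction gives 80.5%. The stated power reproduces, so the rates are usable inputs. The pooled rate is (50 + 25)/2 = 37.5%.

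**Which yes/no outcome?** TTS status cannot vary, because TTS is an enrolment criterion (Protocol 3.1b) and every randomised officer has it. PTS is the obvious candidate, but it is an inference. The NIOSH 15 dB variant and DPOAE-shift status (Protocol 4.0) are also binary.

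**Information kept by a yes/no cut.** For a normal trait cut at a point that gives prevalence p, and a small marker effect, efficiency relative to the uncut trait is φ(z)² / [p(1 − p)], with z = Φ⁻¹(p).

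| PTS rate | φ(z)² | p(1 − p) | Kept | Lost | 132 officers act like |
|---|---|---|---|---|---|
| 50% (placebo) | 0.1592 | 0.2500 | 0.637 | 36.3% | 84 |
| 37.5% (pooled) | 0.1438 | 0.2344 | 0.613 | 38.7% | 81 |
| 25% (ZNS) | 0.1010 | 0.1875 | 0.539 | 46.1% | 71 |

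The mean of the two arms is (36.3 + 46.1)/2 = 41.2%. The loss under this formula is smallest at a 50% rate, so about 36% is its floor for any cut of a normal trait.

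**Check by simulation** (N = 132, PTS rates 50% and 25%, assumed minor allele frequency 0.3, score tests adjusted for arm, 20,000 runs). The loss was 40%, 37% and 35% for per-allele effects of 0.2, 0.4 and 0.6 SD. At 0.4 SD, power at nominal two-sided 0.05 fell from 83% to 63%.

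**Coarse thresholds.** If thresholds are read in 5 dB steps and the shift has an SD of 5 to 10 dB (both assumptions), the loss is 31–35% at a 50% rate, 34–37% at 37.5% and 42–45% at 25%.

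**Power at genome-wide levels.** The documents give no significance threshold, so 1e-5 and 5e-8 are assumptions. Linear-model power at n = 132, for a marker explaining a share R² of the variance, comes from a noncentral F with 1 and 130 degrees of freedom and noncentrality 132 × R²/(1 − R²):

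- R² = 0.05: about 3% at 1e-5 and 0.2% at 5e-8.
- R² = 0.10: about 23% and 3%.
- R² = 0.20: about 85% and 48% (these two by simulation, 1,500 runs).

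A logistic scan, with less information, falls below these values.

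**The case against.** Several counter-arguments have force.

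- **Section 1.4 is narrower than a rejection of binary outcomes.** A reader might take it as one, but it concerns extreme-phenotype sampling and gives loss of sample size as the mechanism. It promises CEP-SKAT, and 12.5 delivers CEP-SKAT. A logistic scan of a clinical endpoint alongside it is conventional. This stands: the tension is with the reasoning in 1.4 and is not a broken commitment.
- **The continuous data are not thrown away.** A reader might infer that the whole pharmacogenetic analysis discards them, or that a variant missed by the scan is barred from CEP-SKAT. The documents say neither: CEP-SKAT uses the continuous shift and all variants are included. What remains is that single-marker ranking and annotation rest on the logistic stage.
- **The formula does not match the traits exactly.** PTS is a shift of at least 10 dB at any frequency from 2 to 6 kHz in at least one ear (SAP 3.2), whereas the proposed trait is an average. This stands, and the figures are approximations.
- **The change may rarely alter a finding.** At R² of 0.10 or less, the linear scan itself usually fails at genome-wide levels. This stands and limits the importance.
- **Extremes only.** A reader might also infer that CEP-SKAT drops genotyped officers who are not in the tails. Neither 12.5 nor SAP 7.1.3 states a cut-off or an exclusion, and neither says whether everyone sampled is genotyped. At most this calls for a clarifying sentence.

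**Conclusion.** The point holds as a matter of efficiency and specification. The scan that ranks markers is logistic, its outcome is unnamed, and a more informative continuous phenotype is already planned. If the outcome is PTS, about 36% to 46% of the information is lost in that stage across the plan's own PTS rates, and 39% at the pooled rate.

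This rests on a normally distributed shift, small marker effects and treating PTS as a cut of one trait. Larger effects or 5 dB steps reduce the loss somewhat. A single figure such as 40 to 45% would be too narrow: under the formula it requires a PTS rate between about 34% and 26%.

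The consequence is minor. Only the single-marker stage of an exploratory analysis is affected, and the primary comparison is untouched.

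**What to change.** In SAP 7.1.3 and Protocol 12.5:

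- Run the single-marker scan as linear regression of the continuous 30-day average threshold-shift Z-score on allele dosage, rank-normalised if skewed. State the frequencies and ears averaged; Protocol 12.2.2 already uses a 3 to 6 kHz average.
- Adjust for the listed covariates that the trial actually collects. Drug concentration is on the list, but neither study calendar (Protocol 9.0, SAP 2.6) schedules a sample for it.
- Keep logistic regression as a supporting check, with PTS named as its outcome.
- Add one sentence saying which genotyped officers enter CEP-SKAT.

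The cost is wording and a change of model in the scan. No new hearing data or visits are needed. The downsides are that effects are reported in dB or SD units instead of odds ratios, and that the scanned trait is an average shift and not the clinical PTS endpoint. The supporting logistic analysis covers that second gap.
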